ALL refractory prior to InO: 
 • Name, start and stop dates, and best response to treatment prior to InO 	✓	✓			
Concomitant medication to InO		✓ (if	✓	✓	

PFIZER CONFIDENTIAL

Variables	Study time points				
	Pre-index observation period	Baseline	Index date	Post-initiation observation period	Other
treatment: • Azole antifungal therapy including fluconazole, voriconazole, itraconazole and posaconazole: date started, date end		medication during InO treatment)			
AEs: name, date start, date end, grade, treatment given and response to treatment: • Documented diagnoses of VOD/SOS • grade 3/4 TRAEs affecting the lung, cardiac system, or kidney		✓		✓	
For each HSCT after initiation of InO: • date • InO treatment completed at HSCT: Yes / No • Conditioning regimens prior to HSCT including Busulfan other alkylating agents (names and date start, date end); full intensity / reduced intensity conditioning • Response to HSCT: CR, CRI, progressive disease, stable disease, alive/dead after HSCT				✓	
Chemotherapy treatment after initiation of InO: • name, regimen, start date • Response to chemotherapy treatment: CR, CRI, progressive disease, stable disease, alive/dead at end of treatment				✓	
CAR-T cell therapy after InO: • start date • response to CAR-T cell therapy: CR, CRI, progressive disease, stable disease, alive/dead at end of treatment				✓	
Patient status at the end of data collection period (alive/dead) • date of death / last clinic visit • Cause of death • If not known (i.e. lost to follow-up),				✓	

Variables	Study time points				
	Pre-index observation period	Baseline	Index date	Post-initiation observation period	Other
date of last recorded hospital visit.					

Note: All dates are DD/MM/YYYY for all patients, except for date of birth (MM/YY). If dates are not available as DD/MM/YYYY, dates will be recorded as MM/YYYY instead.

List 1. Operational definitions for clinical endpoints

Salvage therapy: therapy initiated in patients in whom initial induction therapy does not achieve remission (refractory ALL) or patients who entered remission and then subsequently relapsed (relapsed ALL), with the aim to induce remission of ALL.

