9. HANDLING OF MISSING VALUES

Where dates are ambiguous because of missing day and/or months, standard imputation will be applied: where day is missing the 15th of the month will be assumed; where both day and month are missing the 1st July will be assumed if appropriate to the analysis being conducted. The imputed dates for pre-index records will be reviewed to confirm they are prior to the index date, and the imputed dates for post-index records will be reviewed to confirm they are after the index date. Where data other than dates are missing from the original medical record, the affected analyses will be conducted using only the results of those patients with data available and the number included in each analysis will be stated. The percentage of data missing will be reported for each study variable. Note that the multivariate model will only include those patients with non-missing values for all covariates.

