The proportion of patients achieving MRD negativity overall and by the number of completed cycles will be presented as a binary variable (see [Section 10.1.4](#)), with the denominator being the total number of patients for whom MRD negativity has been assessed and who have achieved CR/CRi, at any time until the end of treatment with InO (defined as the date of recorded discontinuation of InO). The method of MRD negativity evaluation will be presented as a categorical variable (see [Section 10.1.2](#)). This definition of the MRD denominator supersedes the earlier definition detailed in the protocol and earlier in this SAP.

10.2.5. Secondary Objective 4

To describe OS, and cause of death; in all patients and in patient with or without follow-up HSCT.

The number and proportion of patients surviving at 3, 6 and 12 months after InO initiation will be presented as a categorical variable (see [Section 10.1.2](#)). The median OS and 95% CI will also be presented as Kaplan-Meier plots (see [Section 10.1.5](#)). Cause of death will be presented as a categorical variable (see [Section 10.1.2](#)). A summary table of the number of events and censored patients at each month interval will also be included. OS = death or date patient was last known to be alive – index date. OS will be presented in days or years as appropriate. OS in years will be calculated as the OS in days divided by 365.25. If any components required for the calculation are missing or incomplete for a patient, then that patient will be excluded from the analysis.

10.2.6. Secondary Objective 5

To describe RFS in all patients and in patients with or without follow-up HSCT. Additionally, to describe NRM in patients undergoing follow-up HSCT.

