10.2.11. Summary of Analyses

Outcome	Analysis Set	Supports Protocol Objective Number	Subgroups	Statistical Method	Missing Data
Summary of Age at index	All patients	Primary objective	None	Age at index date will be calculated as the difference between index date and date of birth. Summary statistics calculated (as per Section 10.1.1).	Day of birth assumed to be the 15 th of the month. If month is missing, month of birth is assumed to be July, otherwise excluded.
Distribution of sex	All patients	Primary objective	None	Frequency tables and percentages.	Excluded.
Distribution of ECOG performance status at baseline	All patients	Primary objective	None	Frequency tables and percentages. Summary statistics.	Excluded.
Time between ALL diagnosis and initiation of InO (index date)	All patients	Primary objective	None	Frequency tables and percentages. Summary statistics.	Dates will be assumed to be the 15 th of the month. If month is missing, month of birth is assumed to be July, otherwise excluded.
Phase of disease at index date	All patients	Primary objective	None	Frequency tables and percentages.	Excluded.
CD22 expression: percentage of positive cell blasts	All patients	Primary objective	None	Frequency tables and percentages. Summary statistics.	Excluded.
Distribution of ALL cytogenetics	All patients	Primary objective	None	Frequency tables and percentages.	Excluded.
Number of ALL relapses prior to index date	All patients	Primary objective	None	Frequency tables and percentages. Summary statistics.	Excluded.
History of liver diseases prior to index date	All patients	Primary objective	None	Frequency tables and percentages.	Excluded.
Summaries of full blood counts at baseline	All patients	Primary objective	None	Summary statistics.	Excluded.
Summaries of liver function tests at baseline	All patients	Primary objective	None	Summary statistics.	Excluded.
1st line chemotherapy according to national trial or treatment guideline	All patients	Primary objective	None	Frequency tables and percentages.	Excluded.

PFIZER CONFIDENTIAL

Outcome	Analysis Set	Supports Protocol Objective Number	Subgroups	Statistical Method	Missing Data
Summary of number of lines of salvage therapy	All patients	Primary objective	None	Frequency tables and percentages. Summary statistics.	Excluded.
Number of prior HSCTs	All patients	Primary objective	None	Frequency tables and percentages. Summary statistics.	Excluded.

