Distribution of methods used to assess MRD negativity	All patients	Secondary Objective 3	None	Frequency tables and percentages.	Excluded.
Number and proportion of patients surviving at 3,6 and 12 months after InO initiation	All patients	Secondary Objective 4	Overall, and separately in patients with and without follow-up HSCT	Frequency tables and percentages.	Excluded.
Cause of death	All patients	Secondary Objective 4	Overall, and separately in patients with and without follow-up HSCT	Frequency tables and percentages.	Excluded.
Median OS (95% confidence interval)	All patients	Secondary Objective 4	Overall, and separately in patients with and without follow-up HSCT	Kaplan-Meier analysis, median OS measured as being from the date of InO initiation to the date of death. Patients alive at end of follow-up will be censored at date of last visit.	Standard imputation for dates (see Section 7). Otherwise excluded.
Proportion of patients who are relapse free at 3, 6 and 12 months after InO initiation	All patients	Secondary Objective 5	All patients, separately in patients with follow-up HSCT	Frequency tables and percentages.	Excluded.
Median RFS (95% CI)	All patients	Secondary Objective 5	All patients, separately in patients with	Kaplan-Meier analysis, from InO initiation to date of first relapse or date of	Standard imputation for dates (see Section 7).

PFIZER CONFIDENTIAL

Outcome	Analysis Set	Supports Protocol Objective Number	Subgroups	Statistical Method	Missing Data
			follow-up HSCT	last visit before data collection.	Otherwise excluded.
Median NRM (95% CI)	Patients undergoing follow-up HSCT	Secondary Objective 5	None	Kaplan-Meier analysis, from date of follow-up HSCT to date of death or the date of last visit before date of data collection. 95% CI will also be presented.	Standard imputation for dates (see Section 7). Otherwise excluded.
Proportion of patients initiated on each treatment	All patients	Secondary objective 6	Per treatment (chemotherapy (blinatumomab, other). HSCT, CAR T-cell therapy)	Frequency tables and percentages.	Excluded.
Response to treatment	All patients	Secondary objective 6	Per treatment (chemotherapy (blinatumomab, other). HSCT, CAR T-cell therapy)	Frequency tables and percentages.	Excluded.
Survival following treatment	All patients	Secondary objective 6	Per treatment (chemotherapy (blinatumomab, other). HSCT, CAR T-cell therapy)	Frequency tables and percentages.	Excluded.

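### Imputed partial dates are checked only against the index date, so they can precede transplant, and the SAP contradicts itself on whether patients with partial dates are imputed or excluded

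*SAP*

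**What the plan says.** SAP section 9 has two defaults. For a missing day, "where day is missing the 15th of the month will be assumed". For a missing day and month, "where both day and month are missing the 1st July will be assumed if appropriate to the analysis being conducted"; the SAP gives no criterion for when it is appropriate. The order review has two halves. Imputed dates that belong before treatment are checked to lie ahead of the index date. For those that belong after it, "the imputed dates for post-index records will be reviewed to confirm they are after the index date". Nothing says which date is used when the review fails, and no other date is compared. Protocol 9.7 has the same defaults without the qualifier or the review. The note under the dataset table in Protocol Annex 2 foresees the month-only form: "If dates are not available as DD/MM/YYYY, dates will be recorded as MM/YYYY instead".

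The analysis sections differ on whether imputed dates are used at all. For OS (SAP 10.2.5), and again for RFS and NRM (SAP 10.2.6): "If any components required for the calculation are missing or incomplete for a patient, then that patient will be excluded from the analysis". In the summary table (SAP 10.2.11), the missing-data cells for median OS, RFS and NRM begin "Standard imputation for dates (see Section 7"), with exclusion only as the remainder. SAP section 7 is the analysis sets; missing values are in section 9. The row with the Cox model for time to VOD/SOS says only that missing data are excluded.

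NRM is timed from the earliest follow-up HSCT (SAP 10.2.6). SAP section 8, secondary objective 7, includes VOD/SOS occurring after HSCT in patients with a follow-up transplant.

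**The concern.** The index date is the right reference for OS and RFS, which start there. It is the wrong reference for an endpoint that starts at, or is classified by, a later date. Suppose HSCT is on 20 March and the chart gives VOD/SOS, or a relapse or death, only as March. The default is 15 March. That is after the index date, so it passes the review, but it is five days before the transplant. NRM time becomes negative, or the VOD/SOS case drops out of the post-HSCT summary.

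The second problem is that two analysts following the SAP could treat the same patient differently, one imputing and the other dropping the patient. With about 25 patients, each one is 4% of the data, and the choice could be made after the data are seen.

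**Working it through.** The plan states no figure on this point to reproduce. The share of partial dates is not given, so it is varied from 5% to 40%.

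**1. Size of the imputation error** (event equally likely on any day of a 365-day year).
- Day missing: the absolute errors sum to 241 days in a 31-day month, 225 in a 30-day month and 196 in February. Mean = (7×241 + 4×225 + 196)/365 = 2,783/365 = 7.6 days; the range is −16 to +14.
- Day and month missing: 181 days of the year precede 1 July and 183 follow it. Mean = (181×182/2 + 183×184/2)/365 = 33,307/365 = 91 days, about 3.0 months.

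**2. Order relative to HSCT, day missing.** Let the event fall on day *d* of its month, *s* days after HSCT. The imputed date precedes HSCT when 15 < *d* − *s*, that is *d* > 15 + *s*.
- *s* = 7: *d* ≥ 23, so (365 − 12×22)/365 = 101/365 = 28%.
- *s* = 14: *d* ≥ 30, so (11 + 7)/365 = 18/365 = 5%.
- *s* ≥ 16, hence also 21 days: none.

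The date moves back by at most 16 days. With HSCT assumed 60 to 150 days after index, all of these pass the index check.

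**3. Order relative to HSCT, year only.** By the same reasoning the share is (183 − *s*)/365: 48% at 7 days, 42% at 30 and 23% at 100. A simulation of 400,000 records (index dates uniform from June 2016 to September 2020, which is not a whole number of years, and HSCT as above) gives 51%, 44% and 22%. Of all records, 28%, 28% and 21% are misordered and still pass the index check.

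**4. Effect on a Kaplan-Meier median.** Simulation with n = 25, 3,000 replicates and exponential times. The medians are 5.0 and 7.7 months, the PFS and OS medians of the inotuzumab arm quoted in Protocol section 7. Cells give the mean absolute shift in months, with the 95th percentile in brackets; ranges cover the two medians.

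| Partial share | Day missing | Year only |
|---|---|---|
| 5% | 0.01–0.02 (0.07–0.10) | 0.13–0.15 (0.9–1.0) |
| 20% | 0.05 (0.33–0.36) | 0.44–0.49 (1.7–2.1) |
| 40% | 0.09–0.10 (0.39) | 0.70–0.78 (2.2–2.6) |

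**5. What one misfiled case means.** On the rates in Protocol 9.5, 25 × 0.47 = 11.75 patients have HSCT, and 11.75 × 0.22 = 2.6 of them have VOD/SOS. One case is 1/2.6, more than a third of the expected events.

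**6. What bounding can achieve.** For year-only dates at a 20% share, the imputed date was kept between last contact and the year end or cut-off. The mean absolute shift fell only from 0.44 to 0.36 months (median 5.0) and from 0.49 to 0.38 (median 7.7). The mean signed shift rose from +0.10 to +0.30 and from +0.08 to +0.28. Bounds restore valid order; they do not recover the lost information.

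**7. The rules side by side.**

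| Analysis | Section 9 | Analysis text | Table 10.2.11 |
|---|---|---|---|
| Median OS | impute | exclude (10.2.5) | impute |
| Median RFS, NRM | impute | exclude (10.2.6) | impute |
| Time to VOD/SOS | impute | no date rule (10.2.8) | exclude |

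**The case against.** The strongest reply is that sections 10.2.5 and 10.2.6 exclude patients with incomplete components, and the VOD/SOS row excludes too, so imputed dates never reach these analyses. That reading is available, but the summary table says the opposite for the same medians. If exclusion does govern, the problem becomes loss of patients from about 25, possibly including a documented VOD/SOS case that lacks only its day.

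Other parts of the reply stand and limit the point:
- A reader might infer that OS and RFS times can go negative unnoticed. Both start at index, and the review catches that. Only the replacement date is missing.
- A reader might infer that the survival medians are corrupted. For month-only dates, the form Annex 2 foresees, they are not. A mean shift of about 0.1 month is small against a large-sample 95% half-width of roughly 1.96 × (5.0/ln 2)/√25 = 2.8 months, or 4.4 months for a median of 7.7.
- CR/CRi and MRD windows are largely protected, because Annex 2 records response by cycle number.
- The HSCT subgroups in SAP 7.3 are defined by whether a transplant took place, not by event order. The VOD/SOS risk-factor analysis follows patients from index. Only the after-HSCT summary depends on order.
- For time since diagnosis, the summary table says "If month is missing, month of birth is assumed to be July, otherwise excluded", which implies 15 July, not 1 July. It looks like wording carried over from the age row, moves a baseline descriptive by 14 days, and affects no time-to-event result.

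The study is descriptive, with baseline characteristics as its primary objective, so nothing here threatens the main purpose.

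**Conclusion.** The point holds in a limited form. The order review omits HSCT, the date that NRM and the post-HSCT VOD/SOS summary depend on, and there is no rule for a failed review. With a missing day, about 28% of events truly 7 days after HSCT would be placed before it, 5% at 14 days and none at 21. The documents give no onset time relative to HSCT, so these timings are assumptions. The harm is a negative NRM time or a misfiled safety event, and few such events are expected.

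For OS and RFS, month-only dates are negligible. Year-only dates matter if they occur: the mean error is 91 days, which is 60% of a 5.0-month and 39% of a 7.7-month median. The documents do not say how many to expect, and the undefined qualifier leaves open whether they would be imputed at all.

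The conflict between imputing and excluding needs no assumption and should be settled before analysis.

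**What to change.** 1. **One rule.** State in SAP section 9 that partial dates are imputed for OS, RFS, NRM and time to VOD/SOS. Delete the exclusion sentences for incomplete components in 10.2.5 and 10.2.6, and align the VOD/SOS row in 10.2.11. Point the Section 7 references to section 9. Either define when 1 July is appropriate or drop the qualifier.
2. **Bounded dates.** Restrict each imputed date to the interval allowed by its known month or year and by the patient's known dates: index, HSCT, last contact alive, death and cut-off. Apply a bound only where the order follows from the event (a death comes after HSCT and after last contact alive) or is charted (VOD/SOS or relapse before or after HSCT). Keep the 15th or 1 July when it lies in the interval; otherwise use the interval's midpoint. This also supplies the missing rule for a failed check.
3. **Sensitivity.** If any year-only event date is imputed, report OS, RFS and NRM once with the earliest and once with the latest admissible date. This is needed because bounding alone gains little accuracy and shifts the median later on average.

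The cost is SAP wording, a few lines of code and, if triggered, one extra table. The downside is slightly more programming than a fixed day.

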10. STATISTICAL METHODOLOGY AND STATISTICAL ANALYSES

10.1. Statistical Methods

The following statistical methods will be used:

10.1.1. Analysis for Quantitative Data

Quantitative data will generally be analysed using basic summary statistics of central tendency (including numbers, means and medians), number of missing and non-missing values and dispersion (including standard deviations, the interquartile range [IQR] and the range). If data are normally distributed (evaluated through inspection of histograms), 95% confidence intervals will be calculated, otherwise the IQR will be presented instead.

10.1.2. Analysis for Categorical Data

For categorical data, the number, frequency and percentage tables will be presented. The number of missing and non-missing values will be presented.

10.1.3. Analysis for Ordinal Data

For ordinal data, summary statistics of central tendency (including numbers, means and medians), the number of missing and non-missing values and dispersion (including standard deviations, IQRs and the range) will be presented along with frequency and percentage tables.

10.1.4. Analysis for Binary Endpoints

Most binary endpoints will be summarized using frequency tables with numbers, percentages and the number of missing and non-missing values.

10.1.5. Analysis for Time-to-event-data

For survival-related endpoints, Kaplan-Meier analysis will be used where appropriate. Summary tables of the number of events and censored patients at each month interval will also be included.

95% Confidence Intervals for median survival will be estimated using the method of Brookmeyer and Crowley or another appropriate method depending on the statistical programme being used to conduct the analysis. Swimmer plots will be used to show individual patient response to treatment over time (CR, PR, stable disease, progressive disease); these are plots that display a range of information with bars indicating the length of follow-up for each individual patient and symbols on the bars showing where CR and PR are reached and end.

10.2. Statistical Analyses

10.2.1. Primary Objective

To describe the baseline demographic, clinical (including previous treatment) and laboratory characteristics of patients with relapsed/refractory B-cell ALL at initiation of treatment with InO.

Age, duration from ALL diagnosis to index date, CD22 expression, full blood counts and liver function test results will be summarised as quantitative variables (see [Section 10.1.1](#)), measures of central tendency (mean and median) and dispersion (standard deviation, IQR and range) and the number of non-missing and missing values will be calculated. Age at index date will be calculated as the difference between index date and date of birth. As only month and year of birth will be collected for data privacy reasons, the day of date of birth will be inferred as the 15th of the month as per the missing data section (see [Section 7](#)). Sex, phase of disease at index date, ALL cytogenetics, history of liver disease at index date, 1st line chemotherapy according to national trial or treatment guideline and conditioning regimen for each HSCT will be summarised as categorical variables (see [Section 10.1.2](#)). ECOG performance status at index, number of ALL relapses prior to index date, number of lines of salvage therapy, number of prior HSCTs and number of CAR T-cell therapies will be summarised as ordinal variables (see [Section 10.1.3](#)). Whether the patient was treated with blinatumomab will be summarised as a binary variable (see [Section 10.1.4](#)). Overall HSCT rate will be calculated as the number of patients with.

10.2.2. Secondary Objective 1

To describe the InO treatment pathway, including InO doses, dose modifications and number of cycles of treatment; and concomitant medications.

Total duration of treatment with InO will be summarised as a quantitative variable (see [Section 10.1.1](#)); measures of central tendency (mean and median) and dispersion (standard deviation, interquartile range [IQR] and range) and the number of non-missing and missing values will be calculated. The number of cycles of InO per patient, the number of interrupted cycles of InO, doses of InO prescribed and the modification of doses of InO will be summarised as ordinal variables (see [Section 10.1.3](#)). Reasons for interruption and modification of InO cycles andazole antifungal therapies concomitant to InO treatment will be summarised as categorical variables (see [Section 10.1.2](#)). The proportion of patients who temporarily or permanently stopped InO treatment due to an AE will be presented as proportions and percentages.

10.2.3. Secondary Objective 2

To summarise CR/CRi rates following initiation of InO, overall and according to the number of salvage therapies received prior to InO initiation.

The CR/CRi rate will be estimated as the proportion of patients who achieve CR/CRi divided by the total number of patients completing treatment with InO (defined as patients with a recorded date of discontinuation of InO). Patients who have not completed treatment with InO or do not have a recorded discontinuation date will not be included. Patient response to treatment will be presented as a binary variable (see [Section 10.1.4](#)). Response rates will be presented overall and by number of salvage therapies in the pre-index observation period (0,1, ≥ 2). Kaplan-Meier analysis will be utilised to analyse time to CR/CRi and the median time to CR/CRi, as well as 95% CI, will be calculated using the Kaplan-Meier method and presented as per [Section 10.1.5](#).

10.2.4. Secondary Objective 3

To summarise MRD negativity rates following initiation of InO and describe the number of cycles of InO needed to attain MRD negativity.

The proportion of patients achieving MRD negativity overall and by the number of completed cycles will be presented as a binary variable (see [Section 10.1.4](#)), with the denominator being the total number of patients for whom MRD negativity has been assessed and who have achieved CR/CRi, at any time until the end of treatment with InO (defined as the date of recorded discontinuation of InO). The method of MRD negativity evaluation will be presented as a categorical variable (see [Section 10.1.2](#)). This definition of the MRD denominator supersedes the earlier definition detailed in the protocol and earlier in this SAP.

10.2.5. Secondary Objective 4

To describe OS, and cause of death; in all patients and in patient with or without follow-up HSCT.

The number and proportion of patients surviving at 3, 6 and 12 months after InO initiation will be presented as a categorical variable (see [Section 10.1.2](#)). The median OS and 95% CI will also be presented as Kaplan-Meier plots (see [Section 10.1.5](#)). Cause of death will be presented as a categorical variable (see [Section 10.1.2](#)). A summary table of the number of events and censored patients at each month interval will also be included. OS = death or date patient was last known to be alive – index date. OS will be presented in days or years as appropriate. OS in years will be calculated as the OS in days divided by 365.25. If any components required for the calculation are missing or incomplete for a patient, then that patient will be excluded from the analysis.

10.2.6. Secondary Objective 5

To describe RFS in all patients and in patients with or without follow-up HSCT. Additionally, to describe NRM in patients undergoing follow-up HSCT.

